## 9.2 Supportive Care

- 9.21 Hyperphosphatemia is an expected on-target pharmacologic effect of FGFR inhibition. Hyperphosphatemia should be managed with diet modifications, phosphate binders and diuretics, or a dose reduction per the recommendations in Section 8.
- 9.22 Patients should receive full supportive care while on this study. This includes blood product support, antibiotic treatment, and treatment of other newly diagnosed or concurrent medical conditions.

## 10.0 Adverse Event (AE) Reporting and Monitoring

The site principal investigator is responsible for reporting any/all adverse events to the sponsor as described within the protocol. Refer to the adverse event and serious adverse event sections of the protocol for detailed information.

The sponsor/sponsor-investigator is responsible for notifying FDA and all participating investigators in a written safety report of any of the following:

- Any suspected adverse reaction that is both serious and unexpected.
- Any findings from laboratory animal or *in vitro* testing that suggest a significant risk for human subjects, including reports of mutagenicity, teratogenicity, or carcinogenicity.
- Any findings from epidemiological studies, pooled analysis of multiple studies, or clinical studies, whether or not conducted under an IND and whether or not conducted by the sponsor, that suggest a significant risk in humans exposed to the drug.
- Any clinically important increase in the rate of a serious suspected adverse reaction over the rate stated in the protocol or Investigator's Brochure (IB).

## Definitions

### *Adverse Event*

Any untoward medical occurrence associated with the use of a drug in humans, whether or not considered drug related.

### *Suspected Adverse Reaction*

Any adverse event for which there is a reasonable possibility that the drug caused the adverse event.

### *Expedited Reporting*

Events reported to sponsor within 24 hours, 5 days or 10 days of study team becoming aware of the event.

### *Routine Reporting*

Events reported to sponsor via case report forms

### *Events of Interest*

Events that would not typically be considered to meet the criteria for expedited reporting, but that for a specific protocol are being reported via expedited means in order to facilitate the review of safety data (may be requested by the FDA or the sponsor).

## 10.1 Adverse Event Characteristics

**CTCAE term (AE description) and grade:** The descriptions and grading scales found in the revised NCI Common Terminology Criteria for Adverse Events (CTCAE) version 5.0 will be utilized for AE reporting. All appropriate treatment areas should have access to a copy of the CTCAE version 5.0. A copy of the CTCAE version 5.0 can be downloaded from the CTEP web site:

[REDACTED]

- a. Adverse event monitoring and reporting is a routine part of every clinical trial.
- b. Identify the grade and severity of the event using the CTCAE version 5.0.

- c. Determine whether the event is expected or unexpected (see Section 10.2).
- d. Determine if the adverse event is related to the study intervention (agent, treatment or procedure) (see Section 10.3).
- e. Determine whether the event must be reported as an expedited report. If yes, determine the timeframe/mechanism (see Section 10.4).
- f. Determine if other reporting is required (see Section 10.5).
- g. Note: All AEs reported via expedited mechanisms must also be reported via the routine data reporting mechanisms defined by the protocol (see Sections 10.5 and 18.0).

Each CTCAE term in the current version is a unique representation of a specific event used for medical documentation and scientific analysis and is a single MedDRA Lowest Level Term (LLT).

NOTE: A severe AE, as defined by the above grading scale, is NOT the same as serious AE which is defined in the table in Section 10.4.

## 10.2 Expected vs. Unexpected Events

*Expected events* - are those described within the Section 15.0 of the protocol, the study specific consent form, package insert (if applicable), and/or the investigator brochure, (if an investigator brochure is not required, otherwise described in the general investigational plan).

*Unexpected adverse events* or suspected adverse reactions are those not listed in Section 15.0 of the protocol, the study specific consent form, package insert (if applicable), or in the investigator brochure (or are not listed at the specificity or severity that has been observed); if an investigator brochure is not required or available, is not consistent with the risk information described in the general investigational plan.

*Unexpected* also refers to adverse events or suspected adverse reactions that are mentioned in the investigator brochure as occurring with a class of drugs but have not been observed with the drug under investigation.

## 10.3 Assessment of Attribution

When assessing whether an adverse event is related to a medical treatment or procedure, the following attribution categories are utilized:

- Definite - The adverse event is *clearly related* to the agent(s).
- Probable - The adverse event is *likely related* to the agent(s).
- Possible - The adverse event *may be related* to the agent(s).
- Unlikely - The adverse event is *doubtfully related* to the agent(s).
- Unrelated - The adverse event is *clearly NOT related* to the agent(s).

**Events determined to be possibly, probably or definitely attributed to a**

**medical treatment suggest there is evidence to indicate a causal relationship between the drug/device and the adverse event.**

The following hospitalizations are not considered to be SAEs because there is no “adverse event” (i.e., there is no untoward medical occurrence) associated with the hospitalization:

- Hospitalizations for respite care
- Planned hospitalizations required by the protocol or to administer protocol directed treatment
- Hospitalization planned before informed consent (where the condition requiring the hospitalization has not changed post study drug administration)
- Hospitalization for administration of study drug
- Hospitalization for routine maintenance of a device (e.g., battery replacement) that was in place before study entry

\*Report any clinically important increase in the **rate** of a serious suspected adverse reaction (at your study) site over that which is listed in the protocol or investigator brochure as an expedited event.

\*Report an expected event that is greater in severity or specificity than expected as an expedited event

\*An investigational agent/intervention might exacerbate the expected AEs associated with a commercial agent. Therefore, if an expected AE (for the commercial agent) occurs with a higher degree of severity or specificity, expedited reporting is required.

A list of known/expected AEs is reported in the investigator brochure, package insert or the literature, including AEs resulting from a drug overdose.

#### 10.331 Death

- Any death occurring within 30 days of the last dose, regardless of attribution to an agent/intervention under an IND/IDE requires expedited reporting within 24-hours.
- Any death occurring greater than 30 days with an attribution of possible, probable, or definite to an agent/intervention under an IND/IDE requires expedited reporting within 24-hours.
- Reportable categories of Death
  - Death attributable to a CTCAE term.

- Death Neonatal: A disorder characterized by cessation of life during the first 28 days of life.
- Death NOS: A cessation of life that cannot be attributed to a CTCAE term associated with Grade 5.
- Sudden death NOS: A sudden (defined as instant or within one hour of the onset of symptoms) or an unobserved cessation of life that cannot be attributed to a CTCAE term associated with Grade 5.
- Death due to progressive disease should be reported as **Grade 5 “Neoplasms benign, malignant and unspecified (including cysts and polyps) – Other (Progressive Disease)”** under the system organ class (SOC) of the same name. Evidence that the death was a manifestation of underlying disease (e.g., radiological changes suggesting tumor growth or progression: clinical deterioration associated with a disease process) should be submitted.

#### 10.332 Secondary Malignancy

- A *secondary malignancy* is a cancer caused by treatment for a previous malignancy (e.g., treatment with investigational agent/intervention, radiation or chemotherapy). A secondary malignancy is not considered a metastasis of the initial neoplasm.
- All secondary malignancies that occur following treatment with an agent under an IND/IDE to be reported. Three options are available to describe the event:
  - Leukemia secondary to oncology chemotherapy (e.g., Acute Myelocytic Leukemia [AML])
  - Myelodysplastic syndrome (MDS)
  - Treatment-related secondary malignancy
- Any malignancy possibly related to cancer treatment (including AML/MDS) should also be reported via the routine reporting mechanisms outlined in each protocol.

#### 10.333 Second Malignancy

- A second malignancy is one unrelated to the treatment of a prior malignancy (and is NOT a metastasis from the initial malignancy). Second malignancies require ONLY routine reporting.

#### 10.334 Pregnancy

An “Initial Pregnancy Report” must be completed in full and faxed to the ACCRU SAE coordinator at [REDACTED] within 24 hours of discovery of a pregnancy of a subject who has taken the Incyte product (INCB054828) or the pregnancy of a partner for a subject who has taken the Incyte product. The “Follow-up Pregnancy Report Form” must be completed and faxed to the ACCRU SAE coordinator at [REDACTED] within 30 days after delivery, so that Incyte is provided with information regarding the outcome of the pregnancy. The ACCRU SAE coordinator will forward all pregnancy reports to Incyte. If the pregnancy results in any events which meet the serious criteria (i.e., miscarriage or termination), the SAE reporting process needs to be followed and the timelines associated with an SAE should be followed.

“Initial Pregnancy Report” and “Follow-up Pregnancy Report Form” can be found on the ACCRU website.

Prior to obtaining private information about a pregnant woman and her infant, the investigator must obtain consent from the pregnant woman and the newborn infant’s parent or legal guardian before any data collection can occur. A consent form will need to be submitted to the IRB for these subjects if a pregnancy occurs. If informed consent is not obtained, no information may be collected.

*In cases of fetal death, miscarriage or abortion the mother is the patient. In cases where the child/fetus experiences a serious adverse event other than fetal death, the child/fetus is the patient.*

NOTE: When submitting [REDACTED]

[REDACTED] the potential risk of exposure of the fetus to the investigational agent(s) or chemotherapy agent(s) should be documented in the “Description of Event” section. Include any available medical documentation.

## 10.4 Expedited Adverse Event Reporting Requirements for IND/IDE Agents

**10.41 Early Phase 2 Studies:** Expedited Reporting via the **ACCRU Adverse Event Expedited Report Form** for Adverse Events That Occur Within 30 Days of the Last Dose of the Investigational Agent

**FDA REPORTING REQUIREMENTS FOR SERIOUS ADVERSE EVENTS (21 CFR Part 312)**

**NOTE:** Investigators **MUST** immediately report to the sponsor **ANY** Serious Adverse Events, whether or not they are considered related to the investigational agent(s)/intervention (21 CFR 312.64)

An adverse event is considered serious if it results in **ANY** of the following outcomes:

- 1) Death
- 2) A life-threatening adverse event
- 3) An adverse event that results in inpatient hospitalization or prolongation of existing hospitalization for  $\geq 24$  hours
- 4) A persistent or significant incapacity or substantial disruption of the ability to conduct normal life functions
- 5) A congenital anomaly/birth defect.
- 6) Important Medical Events (IME) that may not result in death, be life threatening, or require hospitalization may be considered serious when, based upon medical judgment, they may jeopardize the patient or subject and may require medical or surgical intervention to prevent one of the outcomes listed in this definition. (FDA, 21 CFR 312.32; ICH E2A and ICH E6).

**ALL SERIOUS** adverse events that meet the above criteria **MUST** be immediately reported to the sponsor within the timeframes detailed in the table below.

Hospitalization	Grade 1 and Grade 2 Timeframes	Grade 3-5 Timeframes
Resulting in Hospitalization $\geq 24$ hrs	7 Calendar Days	24-Hour; 3 Calendar Days
Not resulting in Hospitalization $\geq 24$ hrs	Not required	

**Expedited AE reporting timelines are defined as:**

- “24-Hour; 3 Calendar Days” - The AE must initially be reported within 24 hours of learning of the AE, followed by a complete expedited report within 3 calendar days of the initial 24-hour report.
- “7 Calendar Days” - A complete expedited report on the AE must be submitted within 7 calendar days of learning of the AE.

Serious adverse events that occur more than 30 days after the last administration of investigational agent/intervention and have an attribution of possible, probable, or definite require reporting as follows:

**Expedited 24-hour notification followed by complete report within 3 calendar days for:**

- All Grade 3, 4, and Grade 5 AEs

**Expedited 7 calendar day reports for:**

- Grade 2 AEs resulting in hospitalization or prolongation of hospitalization

 For studies using PET or SPECT IND agents, the AE reporting period is limited to 10 radioactive half-lives, rounded UP to the nearest whole day, after the agent/intervention was last administered. Footnote “1” above applies after this reporting period.

Effective Date: May 5, 2011

## Special Instructions:

- Follow site-specific reporting guidelines.
  - Submit the ACCRU Adverse Event Expedited Report Form to ACCRU Safety via email at: [REDACTED] ACCRU Safety will forward to Incyte via email to [REDACTED]
- SAE reports should be for a single subject.
- ACCRU Safety will forward to ACCRU IND Coordinator ([REDACTED]) as appropriate. The ACCRU IND Coordinator will assist the sponsor-investigator in notifying the FDA if required.

## 10.5 Other Required Reporting

10.51 Unanticipated Problems Involving Risks to Subjects or Others (UPIRTSOS) in general, include any incident, experience, or outcome that meets **all** of the following criteria:

1. Unexpected (in terms of nature, severity, or frequency) given (a) the research procedures that are described in the protocol-related documents, such as the IRB-approved research protocol and informed consent document; and (b) the characteristics of the subject population being studied;
2. Related or possibly related to participation in the research (in this guidance document, possibly related means there is a reasonable possibility that the incident, experience, or outcome may have been caused by the procedures involved in the research); and
3. Suggests that the research places subjects or others at a greater risk of harm (including physical, psychological, economic, or social harm) than was previously known or recognized.

Some unanticipated problems involve social or economic harm instead of the physical or psychological harm associated with adverse events. In other cases, unanticipated problems place subjects or others at increased *risk* of harm, but no harm occurs.

Note: If there is no language in the protocol indicating that pregnancy is not considered an adverse experience for this trial, and if the consent form does not indicate that subjects should not get pregnant/impregnate others, then any pregnancy in a subject/patient or a male patient's partner (spontaneously reported) which occurs during the study or within 120 days of completing the study should be reported as a UPIRTSO.

If the event meets the criteria for an UPIRTSO, submit to your IRB as required by your institutional policies.

### 10.52 Baseline and Adverse Events Evaluations

The following pre-treatment symptoms/conditions are to be graded at baseline and adverse events are to be graded at each evaluation using CTCAE v5.0 grading.

System Organ Class (SOC)	Adverse event/Symptoms	Baseline	Each evaluation
General disorders and administration site conditions	Fatigue	X	X
Gastrointestinal disorders	Nausea	X	X
Gastrointestinal disorders	Vomiting	X	X
Gastrointestinal disorders	Diarrhea	# of stools	X
Metabolism and nutrition disorders	Anorexia	X	X
Metabolism and nutrition disorders	Hyperphosphatemia	X	X
Investigations	Alanine aminotransferase increased	X	X
Investigations	Aspartate aminotransferase increased	X	X
Investigations	Alkaline phosphatase increased	X	X
Investigations	Blood bilirubin increased	X	X
Investigations	Platelet count decreased	X	X
Investigations	Neutrophil count decreased	X	X
Blood and lymphatic system disorders	Anemia	X	X

### 10.53 Case Report Forms - Academic and Community Cancer Research United (ACCRU)

Submit the following AEs not specified in Section 10.5

10.531 Grade 2 AEs deemed *possibly, probably, or definitely* related to the study treatment or procedure.

10.532 Grade 3 and 4 AEs regardless of attribution to the study treatment or procedure.

10.533 Grade 5 AEs (Deaths)

10.5331 Any death within 30 days of the patient's last study treatment or procedure regardless of attribution to the study treatment or procedure.

10.5332 Any death more than 30 days after the patient's last study treatment or procedure that is felt to be at least possibly treatment related must also be submitted as a Grade 5 AE, with a CTCAE type and attribution assigned.

## 11.0 Treatment Evaluation Using RECIST Guideline

NOTE: This study uses protocol RECIST v1.1 template dated 2/16/2011. See the footnote for the table regarding measurable disease in Section 11.44, as it pertains to data collection and analysis.

Response and progression will be evaluated in this study using the new international criteria proposed by the revised Response Evaluation Criteria in Solid Tumors (RECIST) guidelines (version 1.1) (Eisenhauer et al., 2009). Changes in the largest diameter (unidimensional measurement) of the tumor lesions and the short axis measurements in the case of lymph nodes are used in the RECIST guideline.

11.1 Schedule of Evaluations: For the purposes of this study, patients should be reevaluated every 9 weeks.

11.2 Definitions of Measurable and Non-Measurable Disease

11.21 Measurable Disease

11.211 A non-nodal lesion is considered measurable if its longest diameter can be accurately measured as  $\geq 2.0$  cm with chest x-ray, or as  $\geq 1.0$  cm with CT scan, or MRI.

11.212 A superficial non-nodal lesion is measurable if its longest diameter is  $\geq 1.0$  cm in diameter as assessed using calipers (e.g. skin nodules) or imaging. In the case of skin lesions, documentation by color photography, including a ruler to estimate the size of the lesion, is recommended.

11.213 A malignant lymph node is considered measurable if its short axis is  $\geq 1.5$  cm when assessed by CT scan (CT scan slice thickness recommended to be no greater than 5 mm).

**NOTE:** Tumor lesions in a previously irradiated area are not considered measurable disease.

#### 11.22 Non-Measurable Disease

11.221 All other lesions (or sites of disease) are considered non-measurable disease, including pathological nodes (those with a short axis  $\geq 1.0$  to  $<1.5$  cm). Bone lesions, leptomeningeal disease, ascites, pleural/pericardial effusions, lymphangitis cutis/pulmonis, inflammatory breast disease, and abdominal masses (not followed by CT or MRI), are considered as non-measurable as well.

Note: 'Cystic lesions' thought to represent cystic metastases can be considered as measurable lesions, if they meet the definition of measurability described above. However, if non-cystic lesions are present in the same patient, these are preferred for selection as target lesions. In addition, lymph nodes that have a short axis  $<1.0$  cm are considered non-pathological (i.e., normal) and should not be recorded or followed.

### 11.3 Guidelines for Evaluation of Measurable Disease

#### 11.31 Measurement Methods:

- All measurements should be recorded in metric notation (i.e., decimal fractions of centimeters) using a ruler or calipers.
- The same method of assessment and the same technique must be used to characterize each identified and reported lesion at baseline and during follow-up. For patients having only lesions measuring at least 1 cm to less than 2 cm must use CT imaging for both pre- and post-treatment tumor assessments.
- Imaging-based evaluation is preferred to evaluation by clinical examination when both methods have been used at the same evaluation to assess the antitumor effect of a treatment.

#### 11.32 Acceptable Modalities for Measurable Disease:

- Conventional CT and MRI: This guideline has defined measurability of lesions on CT scan based on the assumption that CT slice thickness is 5 mm or less. If CT scans have slice thickness greater than 5 mm, the minimum size for a measurable lesion should be twice the slice thickness.
- As with CT, if an MRI is performed, the technical specifications of the scanning sequences used should be optimized for the evaluation of the type and site of disease. The lesions should be measured on the same pulse sequence. Ideally, the same type of scanner should be used and the image

acquisition protocol should be followed as closely as possible to prior scans. Body scans should be performed with breath-hold scanning techniques, if possible.

### 11.33 Measurement at Follow-up Evaluation:

- The cytological confirmation of the neoplastic origin of any effusion that appears or worsens during treatment when the measurable tumor has met criteria for response or stable disease is mandatory to differentiate between response or stable disease (an effusion may be a side effect of the treatment) and progressive disease.
- Cytologic and histologic techniques can be used to differentiate between PR and CR in rare cases

## 11.4 Measurement of Effect

### 11.41 Target Lesions & Target Lymph Nodes

- Measurable lesions (as defined in Section 11.21) up to a maximum of 5 lesions, representative of all involved organs, should be identified as “Target Lesions” and recorded and measured at baseline. These lesions can be non-nodal or nodal (as defined in 11.21), where no more than 2 lesions are from the same organ and no more than 2 malignant nodal lesions are selected.

**Note:** If fewer than 5 target lesions and target lymph nodes are identified (as there often will be), there is no reason to perform additional studies beyond those specified in the protocol to discover new lesions.

- Target lesions and target lymph nodes should be selected on the basis of their size, be representative of all involved sites of disease, but in addition should be those that lend themselves to reproducible repeated measurements. It may be the case that, on occasion, the largest lesion (or malignant lymph node) does not lend itself to reproducible measurements in which circumstance the next largest lesion (or malignant lymph node) which can be measured reproducibly should be selected.
- Baseline Sum of Dimensions (BSD): A sum of the longest diameter for all target lesions plus the sum of the short axis of all the target lymph nodes will be calculated and reported as the baseline sum of dimensions (BSD). The BSD will be used as reference to further characterize any objective tumor response in the measurable dimension of the disease.
- Post-Baseline Sum of the Dimensions (PBSD): A sum of the longest diameter for all target lesions plus the sum of the short axis of all the target lymph nodes will be calculated and reported as the post-baseline sum of dimensions (PBSD). If the radiologist is able to provide an actual measure for the target lesion (or target lymph node), that should be recorded, even if it is below 0.5 cm. If the target lesion (or target lymph node) is believed to be present and is faintly seen but too small to measure, a default value of 0.5 cm should be

assigned. If it is the opinion of the radiologist that the target lesion or target lymph node has likely disappeared, the measurement should be recorded as 0 cm.

- The minimum sum of the dimensions (MSD) is the minimum of the BSD and the PBSD.

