#### 11.432 Evaluation of Target Lesions

- Complete Response (CR): All of the following must be true:
  - Disappearance of all target lesions.
  - Each target lymph node must have reduction in short axis to <1.0 cm.

- Partial Response (PR): At least a 30% decrease in PBSD (sum of the longest diameter for all target lesions plus the sum of the short axis of all the target lymph nodes at current evaluation) taking as reference the BSD (see Section 11.41).

- Progression (PD): At least one of the following must be true:

- At least one new malignant lesion, which also includes any lymph node that was normal at baseline (< 1.0 cm short axis) and increased to  $\geq$  1.0 cm short axis during follow-up.

- a. At least a 20% increase in PBSD (sum of the longest diameter for all target lesions plus the sum of the short axis of all the target lymph nodes at current evaluation) taking as reference the MSD (Section 11.41). In addition, the PBSD must also demonstrate an absolute increase of at least 0.5 cm from the MSD.

- Stable Disease (SD): Neither sufficient shrinkage to qualify for PR, nor sufficient increase to qualify for PD taking as reference the MSD.

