## 13.0 Treatment/Follow-up Decision at Evaluation of Patient

- 13.1 Patients who have CR, PR, or SD will continue treatment per protocol up to 35 cycles. After 35 cycles, patients will go to event monitoring.
- 13.2 Patients who develop PD while receiving therapy will go to the event-monitoring phase.
- 13.3 Patients who go off protocol treatment for reasons other than PD or alternative therapy will go to the event-monitoring phase per Section 18.0.
- 13.4 Event monitoring is every 3 months for 3 years after registration. If patient is still alive 3 years after registration, no further follow up is required.
- 13.5 A patient is deemed *ineligible* if after registration, it is determined that at the time of registration, the patient did not satisfy each and every eligibility criteria for study entry. The patient may continue treatment off-protocol at the discretion of the physician as long as there are no safety concerns, and the patient was properly registered. The patient will go directly to the event-monitoring phase of the study (or off study, if applicable).
  - If the patient received treatment, all data up until the point of confirmation of ineligibility must be submitted. Event monitoring will be required per Section 18.0 of the protocol.

- If the patient never received treatment, On-study material and the Off Treatment Form must be submitted. No further data submission is necessary.

13.6 A patient is deemed a *major violation*, if protocol requirements regarding treatment in cycle 1 of the initial therapy are severely violated that evaluability for primary end point is questionable. All data up until the point of confirmation of a major violation must be submitted. The patient will go directly to the event-monitoring phase of the study. The patient may continue treatment off-protocol at the discretion of the physician as long as there are no safety concerns, and the patient was properly registered. Event monitoring will be required per Section 18.0 of the protocol.

13.7 A patient is deemed a *cancel* if he/she is removed from the study for any reason before any study treatment is given. On-study material and the Off Treatment Form must be submitted. No further data submission is necessary.

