#### 16.322 Progression-free Survival

Progression-free survival (PFS) is defined as the time from study entry to the first of either disease progression or death from any cause, where disease progression is determined based on RECIST 1.1 criteria. PFS will be estimated using the Kaplan-Meier method. The median PFS and corresponding 95% confidence interval will be reported. Patients who do not experience disease progression or death while on protocol will be censored at the last disease assessment date.

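### Section 11.41 does not say that the reference sum for progression (MSD) runs over all post-baseline sums; taken literally with 11.432, target-lesion PD is measured from baseline, not from the smallest sum

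*Combined protocol and SAP*

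**What the plan says.** Section 11.41 defines three quantities. The BSD is the baseline sum. The same sum taken after baseline "will be calculated and reported as the post-baseline sum of dimensions (PBSD"), with no particular visit attached. The third is the reference for progression: "The minimum sum of the dimensions (MSD) is the minimum of the BSD and the PBSD".

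Section 11.432 uses them for different purposes. PR is a decrease of at least 30% from the BSD. PD on target lesions is "At least a 20% increase in PBSD", where PBSD is explained in brackets as the sum "at current evaluation) taking as reference the MSD (Section 11.41"). An absolute condition is added: "the PBSD must also demonstrate an absolute increase of at least 0.5 cm from the MSD". SD is whatever falls short of PR and of PD, with the MSD as reference for the latter.

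Other routes to PD do not use the MSD: a new lesion (11.432, 11.433), unequivocal non-target progression (11.433) and symptomatic deterioration (11.45).

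Sections 11.0 and 16.1 name RECIST 1.1 as the governing criteria. For PFS, Section 16.322 says that "disease progression is determined based on RECIST 1.1 criteria". Section 16.321 counts as clinical benefit any CR or PR within 36 weeks, or SD lasting at least 36 weeks. Treatment follows objective status in Section 13.1: "Patients who have CR, PR, or SD will continue treatment per protocol up to 35 cycles". Under 13.2, patients with PD move to event monitoring. Scans are 9 weeks apart (11.1).

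**The concern.** The MSD is defined from two values, both in the singular, and the only place that ties PBSD to a visit ties it to the current one. Joined together, the two sections make the reference for progression the smaller of baseline and the sum being tested. A sum at or below baseline is then compared with itself. The protocol nowhere mentions the smallest sum to date, so nothing in its own formulas corrects this.

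What is at stake is the date of progression in patients whose target lesions shrink and then regrow. If a site or the database applies the formula literally, PD can be dated later, PFS can be longer, and some patients can be carried as SD through week 36. The two readings can also put the same patient in different categories under 13.1 and 13.2. Several sites submit RECIST measurements, so two careful readers could date PD differently from the same scans. With at most 21 evaluable patients, a few such differences could move the median PFS.

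**Working it through.** The plan gives no figure that depends on the MSD, so there is nothing to reproduce. The check applies the stated PD rule under two readings.

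**Inputs.** From 11.432: PD on target lesions if current sum ≥ 1.2 × MSD and current sum − MSD ≥ 0.5 cm; PR if current sum ≤ 0.7 × BSD. From 11.1: 9 weeks between scans. From 16.2: 21 evaluable patients. The tumour sums below are assumed for illustration.

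- Literal reading: MSD = min(BSD, current PBSD).
- Running minimum: MSD = min(BSD, all earlier PBSDs).

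**Step 1: what the literal reading reduces to.** If current ≤ BSD, then MSD = current, the increase is 0% and 0 cm, and there is no target-lesion PD. If current > BSD, then MSD = BSD. The rule is therefore current ≥ 1.2 × BSD and current − BSD ≥ 0.5 cm. A comparison on 200,000 random pairs of baseline and current sums gave 0 mismatches between this and the literal rule. Since 0.2 × 2.5 = 0.5, the 0.5 cm condition governs when the BSD is below 2.5 cm, and the trigger is then BSD + 0.5 cm.

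**Step 2: PD triggers for a BSD of 10 cm.**

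| Smallest sum | Running minimum (1.2 × smallest) | Literal (1.2 × 10) |
|---|---|---|
| 9 cm | 10.8 cm | 12.0 cm |
| 7 cm | 8.4 cm | 12.0 cm |
| 5 cm | 6.0 cm | 12.0 cm |
| 3 cm | 3.6 cm | 12.0 cm |

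The 0.5 cm condition is met at every trigger shown.

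**Step 3: effect on PFS.** Take BSD 10 cm and successive sums 6, 5, 6, 8, 10, 11.9, 12 cm. On a running minimum, PD comes at the third scan (6/5 = 1.20; 6 − 5 = 1.0 cm). Literally it comes at the seventh (12/10 = 1.20). The gap is (7 − 3) × 9 = 36 weeks. If the sum goes instead from 5 cm to 12.5 cm at the next scan, both readings give PD at that scan and the gap is zero. A new lesion, non-target PD or death at that time also closes the gap.

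**Step 4: effect on clinical benefit.** A patient with a PR at week 9 counts as benefit under either reading. The readings differ for a patient with BSD 10 cm and then 7.5 and 9.5 cm. The best shrinkage is 25%, so there is no PR. At 9.5 cm the change from the smallest sum is 9.5/7.5 − 1 = 27% and 2.0 cm, which is PD on a running minimum. Literally MSD = 9.5 cm, the increase is 0%, and the status is SD. If the sum stays below 12.0 cm through week 36 with no other PD, the patient counts as clinical benefit. Each such patient adds 1/21 = 4.8 percentage points.

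**Step 5: effect on ORR.** The PR threshold uses the BSD and is the same under both readings. The only route to a difference is a first PR recorded after a scan that a running minimum would already have called PD.

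**Step 6: does including the current sum matter?** If the current sum is a new minimum, including it gives an increase of 0% and excluding it gives a decrease, so neither is PD. If it is not a new minimum, the reference is the same. The PD calls are identical.

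**The case against.** The best defence is that the word current is not in the MSD definition. It appears only inside the PR and PD rules of 11.432, where it may serve to pick out one PBSD among several. On that view the PBSD in 11.41 means the post-baseline sums to date. The name of the term supports this, and so does the division of labour in 11.432: PR against the BSD, PD and SD against the MSD. On the literal reading the MSD would be redundant, which authors seldom intend. The protocol also names RECIST 1.1 as the standard three times, and the footnote in 11.44 says that the template was revised to match it.

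This stands as evidence of intent. A reader might infer that the trial chose baseline-referenced progression, or that sites are applying it; the documents support neither. The defence does not remove the defect. Section 11 writes out its own working formulas, and 11.432 sends the reader to 11.41 for the MSD: "taking as reference the MSD (Section 11.41). In addition, the PBSD must also demonstrate an absolute increase of at least 0.5 cm from the MSD". What is found there does not say which sums enter.

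It is also fair to say that PFS is a secondary endpoint reported as a Kaplan-Meier median without a planned test, and that 16.32 uses historical controls only where appropriate. That limits the consequence but leaves the rule as it is.

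**Conclusion.** The rule is wrong as written, in a limited way: applied literally, 11.41 and 11.432 together give a baseline-referenced PD rule for target-lesion measurements, and the MSD loses the separate role that 11.432 gives it. The probable intention is a running minimum, so this is a wording defect with a real risk of misapplication.

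Its size depends on the depth of shrinkage and the pattern of regrowth, and the documents do not say how often either will occur. Three stronger statements that a reader might infer do not follow:

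- That regrowth after shrinkage can never be PD below the baseline trigger. The other routes to PD operate at any target sum.
- That PFS is lengthened by at least one scan interval in every such patient. The minimum is zero.
- That responders inflate the clinical benefit rate. A PR within 36 weeks already counts. Leaving aside the remote sequence in Step 5, only patients whose best shrinkage is under 30% can change the rate.

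Apart from that same sequence, the ORR and the two-stage decision are untouched.

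**What to change.** In 11.41, replace the MSD sentence with: *The MSD is the smallest of the BSD and all PBSDs recorded up to the current evaluation.* Section 11.432 can stay as it is. Confirm that the database derives the MSD from all RECIST measurement forms to date, and that sites apply the same definition. This reconciles 11.41 with 11.432 and with the RECIST 1.1 reference in 16.322, and gives 13.1 and 13.2 one definition of progression to work from.

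The cost is one sentence and a derivation check. No new data are needed, and the sample size and decision rule do not change. Where the literal formula would otherwise have been applied, reported PFS and clinical benefit may be slightly less favourable.
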